Studies such as the Rapamune Maintenance Regimen (RMR) study and the Spare the Nephron Study (STN) have shown some promise in affording protection of renal function by switching in stable renal transplant recipients from a CNI-based regimen to a sirolimus, MMF and prednisone regimen at a defined point of 3-6 months post-transplantation.²⁴⁻²⁶ The rationale therein being that early acute complications attributable to mTOR inhibition along with the confounding effects of early immunologic events would not obfuscate the gains in renal function expected to accrue from minimization of CNI. There remains however a legitimate concern that any immunosuppression-related drug conversions may be associated with a finite, but relevant, acute rejection risk. This theoretical increased risk could either be due to a preexisting but clinically undetected rejection process at the time of switch or rejection that may be occurring *de novo* after the conversion. In this regard, renal biopsies afford a valuable opportunity to demonstrate absence of acute rejection at the time of minimizing CNIs. The renal biopsy also yields an excellent baseline estimate of the burden of chronic histologic damage. When coupled with an implant biopsy, the rate of change of chronic allograft pathology (interstitial fibrosis and tubular atrophy can also be calculated).^{27,28} At the same time, there are currently no robust non-invasive monitoring tools that can be used to determine which particular subject is undergoing either an alloimmune process or a non-immune, drug-induced fibrotic process. There is therefore a need to develop non-invasive clinically useful tools that could eventually permit the clinician to determine the underlying mechanism mediating graft injury and facilitate informed individualization of care.²⁹

We hypothesize that transition from tacrolimus based triple therapy with MMF and steroids in stable renal transplant patients to low intensity tacrolimus, everolimus and prednisone will be associated with improvement in GFR and allograft fibrosis. We will test this hypothesis in the context of a randomized, open label, parallel arm study depicted in the schema below. The primary, secondary, exploratory objectives and endpoints that will be examined are detailed further in subsequent sections.

Objectives:

Primary objectives:

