1. Measure and compare the change in interstitial fibrosis (morphometric analysis of trichrome stained slides) at one-year post-transplant in patients converted to everolimus, low intensity tacrolimus and prednisone versus the standard of care tacrolimus, mycophenolate and prednisone regimen.

Secondary objectives:

1. Measure and compare the estimated GFR (using the 4-variable modified MDRD equation) in patients converted to everolimus, low intensity tacrolimus and prednisone versus the standard of care tacrolimus, mycophenolate and prednisone regimen, both at one year and two years post-transplant.
2. Compare the patient and graft survival rates at one-year post-transplant in each group.
3. Measure and compare the rates of immunosuppressant discontinuation and modification for each group.
4. Measure and compare the incidence of significant immunosuppressant-related adverse drug reactions for each group.
5. Compare the rates of post-transplant infections, including CMV, BK, and admissions to the hospital for infectious causes in each group.

Endpoints 6 through 10 are exploratory:

6. Measure and compare the rates and quantity of *de novo* donor specific antibody formation at one-year post-transplant in each group; this will address the important clinical question of the risk of humorally mediated alloimmune events with CNI minimization.
7. Determine the impact of gene variants for donor APOL1, donor ABCB1, recipient cytochrome P450 3A5, and donor and recipient angiotensin receptor and angiotensin converting enzyme on the primary objectives. This endpoint addresses pathways that could potentially impact outcome but are not measured by traditional risk factors and explanatory variables such as rejection and immunosuppressant concentrations.
8. Examine changes in gene expression and urinary proteomics using high throughput methods on peripheral blood, renal biopsy tissue and urine. The rationale underlying this endpoint is that these markers could yield potential biomarkers that may be used as a companion diagnostic aid in selecting patients at particularly high risk for renal progression or CNI nephrotoxicity.

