Categorical data will be evaluated based on Fisher's Exact and Chi Square tests where appropriate; descriptive statistics will be used for continuous variables to describe the two patient populations and primary outcomes in each group (% change in interstitial fibrosis and eGFR from month 3 to month 12). Student's T-test or comparable non-parametric tests (such as the Wilcoxon Rank Sum test) will be used to compare the groups for these continuous variables. Patients will be analyzed based on an intent-to-treat basis, except when prohibited by lack of follow-up 12 month biopsies. Kaplan-Meier curves with the log rank test will be used to compare patient and graft survival, acute rejection free survival, and *de novo* donor specific antibody free survival. A p-value of <0.05 will be considered statistically significant. Slope change of eGFR from 3 months to 12 months post-transplant will be calculated and compared as well.

For the genomic comparisons, patients will be grouped based on the presence or absence of known single nucleotide polymorphisms and compared for primary outcomes. If significant baseline differences are noted between groups, multivariate analysis will be conducted to control for these differences. Similar analyses will be conducted for change in mRNA expression and change in urinary proteomic excretion between month 3 and month 12.

This will be an intent-to-treat analysis with all patients undergoing randomization included in the final data analysis, even if removed from study or control medication. Patients screened and consented, but not randomized will be tracked for reasons of non-randomization, but will not be followed for clinical outcomes or included in the final analysis. These patients will be

replaced to insure a total of 60 patients (30 in each group) are randomized and followed to meet study power and sample-size.

Sample size and power: A total of 60 patients, 30 *randomized* in each arm, will provide 89% power (alpha=0.05, two-sided) to detect a significant difference in the percent change in the quantity of interstitial fibrosis between groups when comparing the three month and 12-month protocol biopsies. These calculations used the following assumptions: 10% drop out rate for each group (27 patients in each group will have baseline and follow-up biopsies), with a $64\pm41\%$ change in degree of fibrosis in the control arm and a $13\pm71\%$ change in fibrosis in the investigational arm.

Evaluation schedule:

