Assessments		Pre-Txp	Day Post-transplant							Week Post-Txp		Month Post-transplant			
Time Frame			1	2	3	4	5	6	7	2	4	3	4	6	12
RANDOMIZATION												X (10-16 week window)			
History and Physical ²		X								X	X	X	X	X	X
Vital Signs		X	X	X	X	X	X	X	X	X	X	X	X	X	X
Protocol Kidney Biopsy												X			X
Donor Specific Antibody Analysis												X			X
Pregnancy testing ⁷		X	X (anytime between day 1-7)											X	X
Serologies ¹		X													
Laboratory Assessment	CBC and Chem-7 ⁴	X	X	X	X	X	X	X	X	X	X	X	X	X	X
	Total cholesterol, HDL, LDL, triglycerides ³	X										X	X		X
	Spot Urine Protein/Creatinine Ratio											X	X		X
	Tacrolimus levels ⁵			X	X	X	X	X	X	X	X	X	X	X	X
	Everolimus levels											X	X	X	X
Clinical assessment ⁶		X	X	X	X					X	X	X	X	x	X
EKG		X													
Estimated GFR		X	X	X	X	X	X	X	X	X	X	X		x	X
Genomic, RNA and proteomic analysis ⁴												X			X
Applanation tonometry using pulse wave velocity and augmentation index		One Baseline Measurement										X			X

Foot notes:

- Includes testing for CMV, Epstein-Barr, hepatitis B & C and HIV for donor and recipients (from evaluation or within one year pre-transplant if the results were negative at pre-transplant evaluation)
- Within 48 hours prior to transplant
- Fasting for at least 8 hours
- Includes genetic SNP analysis, mRNA expression, and urinary proteomic analysis
- Tacrolimus concentrations will be measured daily during the first week post-transplant once tacrolimus is initiated
- Includes assessments of blood pressure, weight changes, arterial stiffness measurement, adverse events, study drug doses, allograft rejection, infection, need for dialysis, hospitalization, re-transplant status, and other immunosuppressant medications
- Includes pregnancy test for females of child-bearing potential

Key references:

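### The mRNA and proteomic analysis uses only the month 3 to 12 change; the month-3 level, which is collected and which patient selection would need, is never related to later outcome

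*Combined protocol and SAP*

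**What the plan says.** Under Objectives, item 8 is to "Examine changes in gene expression and urinary proteomics using high throughput methods on peripheral blood, renal biopsy tissue and urine". Its next sentence gives the reason: such markers might serve as a "companion diagnostic aid in selecting patients at particularly high risk for renal progression or CNI nephrotoxicity". The list is introduced with "Endpoints 6 through 10 are exploratory".

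The Statistical analysis section first describes the genomic comparison, in which "patients will be grouped based on the presence or absence of known single nucleotide polymorphisms and compared for primary outcomes". It then adds, for the other markers: "Similar analyses will be conducted for change in mRNA expression and change in urinary proteomic excretion between month 3 and month 12". Nothing more is said about how mRNA or urinary protein will be analysed. The outcomes cover the same interval: "primary outcomes in each group (% change in interstitial fibrosis and eGFR from month 3 to month 12".

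In the Evaluation schedule, the row "Genomic, RNA and proteomic analysis" is marked at month 3 and month 12, as is the protocol biopsy row. Section M (Gene Expression) takes tissue mRNA from the biopsies, and section K reads fibrosis on biopsy cortex.

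**The concern.** A marker used to select patients has to be known when the selection is made. In this design that is about month 3, when patients are randomised and the investigational arm is converted. A month 3 to 12 change is complete only at month 12, at the visit that supplies the fibrosis result, and it includes nine months of assigned treatment. An association between marker change and fibrosis change may therefore describe concurrent injury or drug effect. It says little about who was at risk at month 3.

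There is a second loss. A marker that is persistently high in patients who go on to fibrose may hardly change, so its difference carries no signal. This is a kind of marker the rationale of objective 8 would value, and the planned variable can discard it. Because exploratory results decide which candidates go forward to validation, the choice of variable has consequences even though no confirmatory claim rests on it.

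**Working it through.** **Timing.** Set side by side, the parts of the plan give:
- Use named in objective 8: selecting high-risk patients.
- Marker samples: month 3 and month 12.
- Marker variable analysed: month 12 minus month 3.
- Outcome: change from month 3 to month 12.
- Month-3 mRNA or protein level against later fibrosis or eGFR: no analysis found.

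**Evaluable number.** The plan gives no figure for the marker analysis, so its own evaluable number is used. The stated 89% power reproduces: difference 64 − 13 = 51; root-mean-square SD √((41² + 71²)/2) = 57.97; standard error 57.97 × √(2/27) = 15.78; 51/15.78 = 3.23. Power is 89.8% by the normal approximation and 88.7% by the t distribution. This rests on 27 patients per arm with paired biopsies, so n = 54.

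**What the change score detects.** Let M3 and M12 be the marker at the two visits (unit variance, correlation ρ), and let F be the fibrosis change. Then

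corr(M12 − M3, F) = [corr(M12, F) − corr(M3, F)] / √(2(1 − ρ)).

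With ρ = 0.5 the denominator is 1, so the change score sees only the difference between the two correlations. All correlations here are assumptions; the documents give none. Rates are two-sided rejections at 0.05 in 20,000 simulated trials of 54 patients.

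| corr(M3, F) | corr(M12, F) | corr(change, F) | Change score significant | Month-3 level significant |
|---|---|---|---|---|
| 0.4 | 0.4 | 0 | 5% | 86% |
| 0.4 | 0.2 | −0.2 | 31% | 87% |
| 0 | 0.3 | 0.3 | 61% | 5% |
| 0 | 0.4 | 0.4 | 87% | 5% |
| 0 | 0.5 | 0.5 | 98% | 5% |

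A Fisher-z check agrees. For r = 0.4, atanh(0.4) × √51 = 0.4236 × 7.141 = 3.03, and Φ(3.03 − 1.96) ≈ 0.86.

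The first two rows show a useful month-3 marker being missed. The last three show that an association with change implies nothing about prediction from month 3.

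**Why a bare month-3 analysis is not enough.** The month-3 biopsy is also the baseline of the percent change in fibrosis, so a marker that merely tracks month-3 fibrosis will correlate with percent change. Assumptions for this check: log-normal fibrosis, correlation 0.5 between visits, SD of percent change about 57 (the plan's pooled value is 58), and a marker related only to month-3 fibrosis at r = 0.3, 0.4 or 0.5. The unadjusted month-3 level is then significant in about 18%, 28% and 42% of trials. With month-3 fibrosis in the model the rate returns to about 5%.

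**The case against.** The strongest reply is that objective 8 asks to examine changes, and the plan does so. Selection appears only in a hedged rationale for an endpoint labelled exploratory. That stands: the mismatch is with the rationale, not with the operative sentence. A reader might infer that the biomarker component fails its objective or cannot answer its question. The documents do not support that, because a change analysis can still describe drug effect or nominate candidates, and the month-3 samples will exist.

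Second, the planned sentence is ambiguous. It may mean relating marker change to fibrosis change, or comparing marker change between groups as an outcome. On the second reading, the worry about markers that mirror fibrosis falls away. The absence of a month-3 analysis remains on both readings.

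Third, the Study purpose section might seem to call for a baseline selection marker when it asks for "non-invasive clinically useful tools that could eventually permit the clinician to determine the underlying mechanism mediating graft injury". In context it concerns which process a patient is undergoing at the time, so markers measured alongside current histology are relevant. It adds nothing to this point.

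Fourth, the 61% to 98% rates could be read as false positives. They are correct detections of an assumed, real association with change. They would mislead only if reported as evidence for selection, and no section says they will be.

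Fifth, it is tempting to say that the month-3 level rescues patients without a month-12 sample. For fibrosis it does not, since that outcome itself needs the month-12 biopsy. Any gain is limited to eGFR, or to patients lacking only a blood or urine sample.

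Finally, the analysis could be added later. It could, but section M already leaves the mRNA targets to be chosen at analysis, and an unplanned choice of time point would add further freedom.

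**Conclusion.** The point holds as an omission. The stated reason for collecting these markers is patient selection, and the one analysis planned uses a variable that is unavailable when selection would occur and that can cancel a stable risk marker. The month-3 level is collected and not used.

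The size cannot be fixed from the documents. The contrast of 5% against 86% rests on correlations of 0.4 with fibrosis change at both visits and 0.5 between visits; when the month-12 correlation is 0.2 it becomes 31% against 87%. These figures illustrate the mechanism and do not estimate what this trial will see.

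A reader might also infer that the month-3 sample is certainly untouched by study treatment. The schedule does not establish this: randomisation, biopsy, marker samples and everolimus levels share the month-3 column with no order given. The primary comparison, its power and the sample size are not affected.

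**What to change.** In the Statistical analysis section:

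1. Add an exploratory analysis with the month-3 level of each mRNA and urinary protein as the explanatory variable for later fibrosis and eGFR. Adjust for treatment arm and for the month-3 value of the outcome; for example, model month-12 fibrosis on month-3 fibrosis, arm and marker, and eGFR likewise.
2. State whether the month-3 marker samples precede conversion.
3. Keep the month 3 to 12 change as a description of association or drug effect, say which of the two readings is meant, and state that it alone does not support a claim about patient selection.

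The cost is wording and one more model per marker and outcome, with no new sample, visit or patient. The downside is more exploratory tests, which should be labelled as such. With the eight mRNA targets currently proposed, independent tests at 0.05 would give at least one false positive with probability 1 − 0.95⁸ = 34%. Precision is also limited. With 54 patients and 80% power (an assumed target), the smallest detectable correlation is tanh((1.960 + 0.842)/√51) = 0.37 for one marker, or 0.46 with a Bonferroni correction over eight.
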